10.1.5. Classification of Adverse Event Severity and Relationship to Investigational Product

For each recorded AE or SAE, a physician-investigator must make an assessment of severity according to the following criteria:

Mild: An event that is usually transient, requiring no special treatment, and does not generally interfere with the patient’s daily activities.

Moderate: An event that interferes with usual activities of daily living, causing discomfort but poses no significant or permanent risk of harm to the patient. The event is usually ameliorated with additional specific therapeutic intervention.

Severe: An event that interrupts usual activities of daily living or significantly affects clinical status. The event poses a significant risk of harm to the patient and hospitalization (prolonged) may be required, and typically requires intensive therapeutic intervention.

Life-threatening: An event that puts the patient into imminent risk of death without intervention.

The severity of application site reactions will be scored as shown in [Table 4](#).

Table 4: Severity Rating Scale for Application Site Reactions

Reaction	Grade 0	Grade 1 - mild	Grade 2 - moderate	Grade 3 - severe
Erythema	None	Target lesions covering <10% BSA ^a and not associated with skin tenderness	Target lesions covering 10 - 30% BSA and associated with skin tenderness	Severe or medically significant but not immediately life-threatening; IV intervention indicated

Reaction	Grade 0	Grade 1 - mild	Grade 2 - moderate	Grade 3 - severe
Rash	None	Macules/papules covering <10% BSA with or without symptoms (e.g., pruritus, burning, tightness)	Macules/papules covering 10 - 30% BSA with or without symptoms (e.g., pruritus, burning, tightness); limiting instrumental ADL; rash covering > 30% BSA with or without mild symptoms	Macules/papules covering >30% BSA with moderate or severe symptoms; limiting self-care ADL
Pruritus	None	Mild or localized; topical intervention indicated	Widespread and intermittent; skin changes from scratching (e.g., edema, papulation, excoriations, lichenification, oozing/crusts); oral intervention indicated; limiting instrumental ADL	Widespread and constant; limiting self-care ADL or sleep; systemic corticosteroid or immunosuppressive therapy indicated

^a Abbreviations: ADL = activities of daily living, BSA=body surface area. The above scale is taken from the National Cancer Institute Common Terminology Criteria for Adverse Events Version 5.0.

The investigator must make an assessment of relationship of the AE to the investigational product based on the following criteria:

Unrelated: The patient did not receive the investigational product, the temporal sequence of the AE/SAE onset relative to administration of the investigational product is not reasonable, or there is another obvious cause of the AE/SAE.

Unlikely: There is evidence of exposure to the investigational product but there is another more likely cause of the AE/SAE.

Possible: There is evidence of exposure to the investigational product, the temporal sequence of the AE/SAE onset relative to administration of the investigational product is reasonable, but the AE/SAE could have been due to another equally likely cause.

Probable: There is evidence of exposure to the investigational product, the temporal sequence of the AE/SAE onset relative to administration of the investigational product is reasonable, and the AE/SAE is more likely explained by the investigational product than by any other cause.

Definite There is evidence of exposure to the investigational product, the temporal sequence of the AE/SAE onset relative to administration of the investigational product is reasonable, the AE/SAE is more likely explained by the investigational product than by any other cause, and the AE/SAE shows a pattern consistent with previous knowledge of the investigational product or investigational product class.

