3.1. Preventative Measures for Surgical Site Infections- Skin Preparation Agents

Chlorhexidine gluconate is a commonly used microbicide. Effective against bacteria and parasites, it has been shown to be more effective against fungi and biofilms than iodine, but less effective against germinating spores.

a pre-packaged swab of 2% chlorhexidine /70% isopropyl alcohol is commonly used brand of surgical skin preparations and is the comparator product in this study.

One disadvantage of chlorhexidine is that hypersensitivity reactions have been reported in 3.2% of men, and 1.9% of women in a sample of 2061 subjects [REDACTED]. A review of the literature found 40 documented cases of anaphylaxis due to chlorhexidine exposure, of which, 85% were male [REDACTED]

3.2.

Zurex Pharma, Inc. (Zurex) has developed [REDACTED] Isopropyl Alcohol (70% v/v) Solution as an antiseptic/antimicrobial agent used to aid in the reduction of infective agents (ie, microorganisms) found among a patient's own skin flora. Effective skin antisepsis is essential in preventing or reducing the incidence of healthcare-associated infections occurring with surgical procedures. The [REDACTED] applicator, containing [REDACTED] solution is FDA approved as a preoperative skin preparation solution for use in pre-surgical settings as an antiseptic/antimicrobial agent to help reduce the bacteria that potentially can cause skin infection.

[REDACTED] This product, called [REDACTED] applicator is the subject of this clinical trial.

Applicator is composed of

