10.1.3. Methods/Timing for Assessing, Recording, and Analyzing Safety Endpoints

AEs will be assessed starting after the first administration of investigational product until the final follow-up at Day 30. General symptoms will be collected via an open ended question: How have you been feeling since the last time we spoke? Elicited AEs will be assessed as described in section [10.1.4](#).

AEs will be documented in the medical/source records, and recorded on the eCRF using accepted medical terms and/or the diagnoses that accurately characterize the event. When a diagnosis is known, the AE term recorded on the eCRF will be the diagnosis rather than a constellation of symptoms. The investigator will assess all AEs for seriousness, relationship to investigational product, and severity. When an event has not resolved by study closure, it will be documented on the AE CRF as “ongoing”.

All AEs, including clinically significant abnormal findings on laboratory evaluations, regardless of severity, will be followed by study physicians until satisfactory resolution (the event either resolved or stabilized and is not expected to resolve in the near term). At the follow-up telephone contact, AEs will be recorded and followed to resolution only if they are serious, or if the study physician assesses them to be clinically significant.

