10.1.4. Elicited Adverse Events

In addition to asked the open ended question regarding AEs, local application site reactions will be assessed by physical examination or querying the patient. These include the appearance of erythema or rash, or patient reported pruritus (itching).

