10.10. Patient Disposition

A patient disposition eCRF will be completed for all patients who are randomized to the study. This eCRF will be used to record the following data:

1. Completion status:
 - a. Patient completed full study (i.e., telephone contact was made at Day 30).
 - b. Patient was lost to follow-up prior to Day 30.
 - c. Patient died before Day 30.
 - d. Patient withdrew consent to continued participation in the study prior to Day 30 (with reason if known).
2. Date of release from the hospital

11. Statistical Methods and Determination of Sample Size

A formal statistical analysis plan (SAP) will be finalized prior to locking the database and commencing with the analysis.

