11.6. Safety Endpoints

11.6.1. Adverse Events

AEs will be coded using the most recent version of the Medical Dictionary of Regulatory Activities (MedDRA) preferred terms and will be grouped by system, organ, and class (SOC) designation by treatment group. The severity, frequency, and relationship of AEs to investigational products will be presented by preferred term by SOC grouping. Listings of each individual AE including start date, stop date, severity, relationship, outcome, and duration will be provided. Each AE (based on preferred terminology) will be counted once only for a given study patient. If the same AE occurred on multiple occasions, the highest severity and relationship to investigational product will be assumed. Thus, study participants are not counted multiple times in a given numerator in the calculation of frequencies for a specific AE. The frequency and severity of skin irritation or allergic reactions at least possibly attributed to each product will also be presented.

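### The SAP leaves out the protocol's summary of product-attributed skin and allergic reactions, and Table 4 gives ordinary redness no mild or moderate grade

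*Protocol*

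**What the plan says.** **Objective.** Protocol 4 and SAP 3.1.2 both make the rate of product-attributed skin irritation or allergic reaction a primary safety objective.

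**Planned summary.** Protocol 11.6.1, like the synopsis, states: "The frequency and severity of skin irritation or allergic reactions at least possibly attributed to each product will also be presented". For an event that recurs in one patient, the same paragraph takes both the worst severity and the strongest relationship.

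**SAP text.** SAP 2 says that the SAP builds on the protocol's plan and holds every planned analysis. SAP 8.6.1 repeats most of 11.6.1 but not the sentence above. It adds a by-arm tabulation of elicited events, and its repeat-event rule mentions severity only.

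**SAP table titles (Section 10).** Tables 16, 17 and 19 show relationship for all adverse events. Table 20 shows elicited events by maximum severity, with no relationship in its title.

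**Severity scales.** Protocol 10.1.3 says "The investigator will assess all AEs for seriousness, relationship to investigational product, and severity". For each recorded event, 10.1.5 requires that "a physician-investigator must make an assessment of severity according to the following criteria", and a mild to life-threatening scale follows. It then adds: "The severity of application site reactions will be scored as shown in" Table 4. Protocol 10.1.4 names erythema, rash and pruritus as the elicited application site reactions. In Table 4, erythema Grade 1 is for non-tender target lesions under 10% of body surface, and Grade 2 is "Target lesions covering 10 - 30% BSA and associated with skin tenderness". Grade 3 names no lesion type but needs a severe or medically significant event.

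**The concern.** There are two gaps, and both bear on the primary safety objective.

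First, the SAP states the objective but gives it no analysis of its own. Someone programming from the SAP alone would produce relationship for all events and severity for elicited events, but never the two together for skin and allergic reactions, counted by patient. Systemic allergic reactions, which protocol 7.6 says are recorded, have no table of their own among the visible titles. If the rate is assembled later, the choice of terms and of attribution rule could be made with the data in view. Protocol 3.1 presents hypersensitivity as a disadvantage of the comparator's chlorhexidine, so this rate matters to how the two products are compared.

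Second, the scale assigned to erythema, the first elicited reaction named, has no mild or moderate place for redness without target lesions. Table 20 then needs a rule for such events, and none is visible.

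**Working it through.** The plan gives no figure to reproduce. SAP 5 rules out hypothesis tests, and SAP 6 calls the 200 patients a convenience sample. The check is a comparison of texts, an enumeration and a small scale calculation.

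**1. Protocol 11.6.1 against SAP 8.6.1 and the table titles**

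- Coding and grouping by system organ class and preferred term: in both.
- Severity, frequency and relationship for all events: in both; Tables 16, 17 and 19 serve the relationship part.
- Individual event listings: in both.
- One count per patient per preferred term: in both.
- Recurrent event, worst severity: in both.
- Recurrent event, strongest relationship: protocol only.
- Skin and allergic reactions at least possibly attributed, with severity: protocol only; no visible title.
- Elicited events by arm: SAP only (Table 20), with no attribution in the title.

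**2. Can the listed tables supply the rate?** A patient may appear under more than one preferred term. If a, b and c patients have attributed erythema, rash and pruritus, the number with at least one lies between max(a, b, c) and a + b + c. The rows alone do not fix it. The individual listings do, once someone has chosen a term list and a rule for recurrent events.

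**3. Erythema row of Table 4.** Cross three area bands (under 10%, 10–30%, over 30% of body surface) with target lesions or plain redness and with tender or not tender: 3 × 2 × 2 = 12 combinations.

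- Target lesions, under 10%, not tender: Grade 1.
- Target lesions, 10–30%, tender: Grade 2.
- Target lesions, under 10% and tender, or 10–30% and not tender: neither grade.
- Target lesions over 30%, tender or not: neither grade.
- Plain redness, all 6 combinations: neither grade.

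Grades 1–2 therefore cover 2 of 12 combinations: 2 of 6 for target lesions and 0 of 6 for plain redness. Within the two area bands that the row names, the counts are 2 of 4 and 0 of 4. The other combinations reach a grade only if the event is judged severe or medically significant (Grade 3).

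**4. Scale of the effect.** One patient in an arm of 100 is 1/100 = 1 percentage point. For context, protocol 3.1 says that "hypersensitivity reactions have been reported in 3.2% of men, and 1.9% of women in a sample of 2061 subjects". If those rates applied to one arm, 100 × 0.019 = 1.9 and 100 × 0.032 = 3.2, so about 2 to 3 patients. Exact 95% limits are 0–3.6% for 0/100 and 0.6–8.5% for 3/100. At such counts, one or two patients attributed or graded differently would change the reported rate visibly.

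**The case against.** The strongest reply is that little is lost. Protocol 11.6.1 still requires the summary, and the SAP's silence does not withdraw it. SAP 8.6.1 lists every event with severity and relationship, and SAP 8.1 puts all data in listings, so with 200 patients the rate can be counted. The shell bodies are not visible, so Table 20 could hold a suitable row or footnote. All of this stands. It limits the consequence, but it does not supply the missing analysis or its term list.

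A reader might infer more than the documents support:

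- **That the severity of ordinary redness is lost.** It is not: the general rating in 10.1.5 applies to each recorded event.
- **That nothing says which scale feeds Table 20.** Protocol 10.1.4 and 10.1.5 read together point to Table 4. What is missing is a fallback for erythema that fits no grade.
- **That the SAP cancels the strongest-relationship rule.** It is silent; the protocol rule remains.
- **That the published rate would be inflated several-fold.** That needs someone to add preferred-term rows, which no document proposes, and needs reacting patients to have several terms each. Protocol 10.1.3 prefers a diagnosis to its separate symptoms, which makes this less likely.

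The rates in step 4 are weak as a forecast. The visible text does not describe the sample they come from, and protocol 7.3.2 excludes patients with known chlorhexidine allergy.

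**Conclusion.** The point holds in two parts. (a) A summary planned in the protocol for a primary safety objective is absent from SAP 8.6.1 and from every visible table title, and the rule on strongest relationship was shortened away with it. (b) The scale assigned to elicited application site reactions gives ordinary redness no mild or moderate grade, and also misses some target lesions.

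The effect falls on a reported safety rate and its severity breakdown, at 1 percentage point per patient per arm; no test or efficacy result is touched. The combination counts describe the scale, not how many patients will fall in each cell, which the documents do not allow one to estimate. Part (a) is limited to visible text. Part (b) takes Table 4 as printed; whether it matches the external scale it cites was not checked and is not relied on. This should be fixed before database lock, but it does not threaten the validity of the trial.

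**What to change.** **SAP 8.6.1, analysis.** Restore the protocol 11.6.1 sentence and the rule that a recurrent event takes the strongest relationship as well as the worst severity. Add one table on the safety set, by treatment received: the count and percentage of patients with at least one skin irritation or allergic reaction rated possible, probable or definite, by maximum severity. Define the reactions as erythema, rash, pruritus and a list of allergic-reaction preferred terms fixed before database lock. The timing is natural, since protocol 11 says that the SAP "will be finalized prior to locking the database and commencing with the analysis".

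**Severity scale.** Keep Table 4 as the scale for SAP Table 20. The sponsor should reconcile its erythema row with the erythema elicited under 10.1.4. State that erythema fitting no Table 4 grade is shown under the general 10.1.5 rating and flagged as such.

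**Cost.** A few sentences in the SAP, one clarifying sentence for protocol 10.1.5, one extra table and a term list to agree before lock. Relationship and general severity are already required for every adverse event, so no new data should be needed. Confirm that the eCRF holds the general rating for these three reactions; if it holds only the Table 4 grade, the fallback would need that field.

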10.1.6. Outcomes and Actions Taken

For each recorded AE or SAE, the investigator must make an assessment of outcome at the time of last observation, as follows:

Fatal: The patient died.

Resolved without Sequelae: The AE or SAE has ended.

Resolved with Sequelae:	The AE or SAE has ended but changes are noted from baseline.
Unresolved – Ongoing:	The AE has not ended and is ongoing at the end of the reporting period or the investigator deems that further follow up is not medically required
Unknown – Lost to Follow-up:	Lost to follow-up at least 2 repeated, documented (15 days apart) unsuccessful attempts to contact the patient.

In addition, if the AE was treated (medications or other physical measures), this will also be recorded.

10.1.7. Reporting Serious Adverse Events

10.1.7.1. 24-hour Reporting Requirements (Initial Report)

Any SAE, including death due to any cause, which occurs to any patient from the time of signing consent through the final follow-up telephone call whether or not related to the investigational product, must be reported **within 24 hours** of knowledge of the event by completing the AE/SAE eCRF. This will trigger an automatic notification of the SAE via an email communication to Zurex and [REDACTED]. [REDACTED] will notify the Medical Monitor upon receipt of the notification and coordinate communications with the Medical Monitor.

10.1.7.2. 3-Day Supporting Documentation Requirements

Written documentation for all SAEs must be received by Zurex and [REDACTED] within 3 business days of reporting the event. Required eCRFs that must be completed include the following:

- AE/SAE eCRF (revised if additional information is available)

In addition, scanned copies of the following may be requested to be uploaded to the data management system.

- Copies of medical records/source documents pertinent to the event (laboratory reports, ECG tracings, medical chart notes, etc.). These should be identified only by Patient number and not include any patient identification information prohibited by Health Insurance Portability Accountability Act (HIPAA).
- Any other relevant information necessary to support the investigator's judgment regarding the SAE's relatedness severity to the investigational product OR by request of the Medical Monitor/Alternate.

These paper documents may be submitted by facsimile, as email attachments, or by attaching them to the patient's eCRF casebook in the electronic data management system (EDMS).

10.2. Demographics

Demographics data include the patient's age, gender, race, and ethnicity. These data will be collected by site staff on a source document and onto an eCRF.

10.3. Eligibility Checklist

An Eligibility Checklist which includes all inclusion and exclusion criteria will be reviewed in after screening measures are completed and on the day of surgery prior to randomization on Study Day 1. If the patient is not eligible for the study, the reasons for ineligibility will be recorded on an eCRF. These patients will be considered screen failures.

10.4. Locator Form

After signing informed consent, patients will be asked to provide names, addresses, and phone numbers of several friends and/or family members who can be contacted if the patient cannot be located (Locator Form). This locator form will be used to assist in contacting patients after hospital discharge and at the final follow-up. This form asks patients his/her name, address, and phone number and to provide names, addresses, and phone numbers of several friends and family members who can be contacted if the patient cannot be located. This information is essential and will be collected during screening, and will be updated on the day of hospital discharge, if needed. This information will remain exclusively at the site.

10.5. Medical History

Medical history will be reviewed during screening to determine patient eligibility and also to record any past or current medical conditions including the reason for the planned surgery and the type of surgery that is anticipated. Any allergies to medications including [REDACTED], isopropyl alcohol, or other excipients in [REDACTED] Solution will also be recorded. Medical history findings will be reported on an eCRF. Childbearing potential in females and if currently breastfeeding will be recorded. Females of childbearing potential will have a pregnancy test. Pregnant or breastfeeding females will be excluded from the study.

10.6. Medications

Antibiotics taken up to 4 days prior to surgery or throughout the study until Day 30 will be recorded including the indication (i.e., prophylaxis or to treat an AE), start and stop dates, dose, route and frequency and will be reported on an eCRF.

10.7. Physical Examination

An appropriate pre-surgical physical examination will be conducted as part of screening and any relevant findings will be recorded. Post-surgical physical examinations will include signs of surgical site or other infection and other AEs such as local application site reactions (erythema, or rash). These data will be recorded on a medical record and an eCRF.

10.8. SSI Diagnosis

A study physician will evaluate the patient and medical records for evidence of SSI up to Day 30. A determination of the type of SSI (Superficial Incisional SSI, Deep Incisional SSI, and Organ/Space SSI) will be made in accordance with CDC criteria as summarized in [Appendix B](#).

10.9. MCW/Froedtert Hospital Standard Preoperative Surgical Skin Prep Instructions

MCW/Froedtert Hospital has Standard Preoperative Surgical Skin Prep Instructions/Procedures for patients undergoing surgery that include use of an antiseptic agent before and/or the day of surgery. Additionally, the surgical pre-op staff follows standard preoperative surgical skin prepping orders the day of surgery. As per the MCW/Froedtert Hospital's standard operating skin prepping procedures, this data will be recorded in the patients eCRF.

